5. TARGET POPULATION

Inclusion criteria:

- All women aged 18 or greater undergoing transvaginal surgery for stress urinary incontinence (index surgery) with or without mesh implantation
- EHR-Based study date range 2010-2019
- Inpatient or outpatient visit

Exclusion criteria:

- No primary care, ob/gyn, or urology visits in the year prior to the surgery
- Prior pelvic organ prolapse surgery
- Prior stress urinary incontinence surgery
- Prior surgery diagnosis of a urethral diverticulum ICD-9-CM code 619.0 or any urinary-genital tract fistula (codes 599.1 and 599.2) in the 90 days prior to the index surgery.

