Next, if the characterization of the data is sufficient for the task, we will pursue a Cox proportional hazards model analysis, with each of the outcomes assessed from the time of the surgery as a time-to-event. We will censor the time-to-event analysis with death or loss to follow-up, defined as a time period >2 years from last applicable encounter of primary care, Obstetrics & Gynecology, or Urology. The models will first be developed at each institutional separately using LASSO Cox to predict time to event for each of the outcomes of interest. We will use the variables retained in any of the individual site models, and develop a Cox model using the method described by Lu and colleagues (WebDISCO) that uses a distributed analysis approach to obtain an exact model solution without sharing case level data (only intermediate and aggregate model coefficients and matrices)¹. This method is being used to protect patient data by processing it at the local institutions and only sharing intermediate modeling statistics (aggregates) between sites.

Because bootstrapping combined with the distributed analysis method would be computationally intensive, we will utilize 10-fold cross validation across all sites for internal validation of the risk model. We assessed overall discrimination using Harrell's concordance statistic (C-statistic). To provide calibration assessments, we will also evaluate the model at fixed time points of 1 year and 2 year for each outcome using the AUC and the Estimated Calibration Index (ECI). The ECI looks at the squared difference between the predicted probability and an estimated observed probability, ranging between 0 and 100, with 0 meaning perfect calibration. Additionally, we will graphically analyze calibration by investigating the smoothed observed-to-predicted probability plot.

Target Population:All women aged 18 or greater undergoing transvaginal surgery for stress
urinary incontinence with or without mid-urethral mesh sling implantation
are eligible for inclusion in the EHR data. Determination of the appropriate
mesh exposure during surgery will be determined through administrative
CPT procedure codes, as defined in the appendix. No exclusions will be
applied based on race or ethnicity. As a separate sensitivity analysis to
reduce potential lack of outcome ascertainment, we will exclude all
patients that do not also have continuity of care within the data site,

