defined as requiring at least one outpatient medicine specialty or relevant
(Obstetrics & Gynecology, Urology) sub-specialty encounter in the 12
months prior to implantation. For this sensitivity analysis, we will also
exclude patients with prior pelvic organ prolapse or stress urinary
incontinence surgeries. As an additional comparator population, we will

Synthetic Mid-Urethral Slings for Stress Urinary Incontinence in Women	
Protocol 1	

	identify all those who underwent a procedure for SUI but did not receive mesh implantation.
Description of Sites/Facilities:	The Participating Sites for this Study include Vanderbilt University Medical Center, Lahey Hospital & Medical Center, Mayo Clinic, Weill-Cornell, and Yale New Haven Health System. In addition, as a data quality validation check, we will have access to a manually collected and curated 3,472 patient case series at Mayo Clinic from 2002 to 2012 of patients that underwent surgery for incontinence ² . For the routine EHR data sources, the valid dates will be from 2010 to the most recently available data.
	As a preliminary assessment of data volume, each site queried their data for CPT 57288 sling operation for stress incontinence. VUMC had a total of 6,106 from 2010-2018, and an average of ~500 cases a year for the last 4 years. Mayo Clinic had a total of 5,413 cases from 2010-2018, and an average of ~500 cases a year for the last 4 years. Weill-Cornell had 887 cases from 2010 to 2019, and an average of 150 procedures a year over the last 4 years. Yale New Haven Healthcare System has data from 2013-2018, and about 170 procedures in the most recent 6-month period. Lahey Clinic had 108 surgeries in 2018, and an average of 84 procedures a year over the last 4 years.
Description of Study Intervention:	This is an observational study design, and there are no direct interventions for patients, thus a Data and Safety Monitoring Plan is not required, and a Data and Safety Monitoring Board is not required.
Study Duration:	1 year, Start Date 02/17/2020, End Date 03/15/2021.
Duration of Data Captured:	2010-2019 in EHR Data

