8. DATA QUALITY

We will access the routinely collected observational data from electronic health records at Vanderbilt University Medical Center, Lahey Hospital & Medical Center, Mayo Clinic, Weill-Cornell, and Yale New

Version 2.0 [15 July 2020]

Haven Health System for this study. In addition, we will have access to a manually collected and curated 3,472 patient case series at Mayo Clinic from 2002 to 2012 of patients that underwent surgery for incontinence, which will be used exclusively to validate the data quality of the electronic health record data extraction and transformation process for the overlapping time period (2002-2012). For the routine EHR data sources, the valid dates will be from 2010 to the most recently available data.

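### The synopsis and Section 5 define the main cohort in two incompatible ways, and nothing in the protocol says which one governs

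*Protocol*

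**What the plan says.** Two current parts of the protocol describe who is analysed.

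- **Synopsis, Target Population.** Every adult woman having transvaginal surgery for SUI, with or without a mesh sling, is eligible. The continuity-of-care restriction is introduced with "As a separate sensitivity analysis to" reduce missed outcomes. In that same sensitivity analysis the study will also "exclude patients with prior pelvic organ prolapse or stress urinary" incontinence operations.
- **Section 5, Exclusion criteria.** Three entries stand without qualification: "No primary care, ob/gyn, or urology visits in the year prior to the surgery", "Prior pelvic organ prolapse surgery" and "Prior stress urinary incontinence surgery". No sensitivity analysis is mentioned. A fourth entry, limited to the 90 days before surgery, reads "Prior surgery diagnosis of a urethral diverticulum ICD-9-CM code 619.0 or any urinary-genital tract fistula (codes 599.1 and 599.2"). It appears only here and gives ICD-9 codes only.

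On data dates, Section 8 says: "For the routine EHR data sources, the valid dates will be from 2010 to the most recently available data". The synopsis adds that "Yale New Haven Healthcare System has data from 2013-2018". Section 5 uses 2010-2019 as the study date range.

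**The concern.** Every outcome rate and every Cox or LASSO model rests on this denominator, and Section 10.2 says the FDA means to use the results in regulatory decisions. The two candidate cohorts differ in ways that bear on the results. Women without a recent visit at the site are those whose later outcomes the synopsis fears will be missed. Women with earlier prolapse or SUI surgery may bring problems from the earlier operation. If the choice is left to whoever writes the extraction code, it may be made silently, or after counts have been seen.

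**Working it through.** No arithmetic applies to the main point, and the protocol states no figure to reproduce. The check sets the texts side by side and follows each reading through.

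| Restriction | Synopsis | Section 5 |
|---|---|---|
| Visit in the prior year | sensitivity analysis only | study exclusion |
| Prior prolapse surgery | sensitivity analysis only | study exclusion |
| Prior SUI surgery | sensitivity analysis only | study exclusion |
| Fistula/diverticulum, 90 days | not mentioned | study exclusion |
| Visit types that count | outpatient medicine specialty, Ob/Gyn, Urology | primary care, Ob/Gyn, Urology |
| Visit window counted back from | implantation | surgery |

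**Does another section decide it?** No.
- Section 4 speaks of identifying all patients with a sling, which leans towards the synopsis, but it also refers to inclusion and exclusion variables.
- The appendix lists cystocele and rectocele repair under the prior-surgery covariate. Under Section 5 that item would be nearly constant, which again leans towards the synopsis without settling it.
- Section 9.1 describes the analyses without naming a population or this sensitivity analysis.

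**If Section 5 governs.** Women failing the visit rule or with prior surgery are already out. The synopsis sensitivity analysis can then remove further women only through the small difference in visit wording. It is close to a copy of the main analysis, and agreement between the two would say almost nothing about missed outcomes.

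**If the synopsis governs.** Women with an earlier sling are in the main cohort.
- The appendix identifies erosion and removal by general diagnosis and procedure codes, and Section 11 expects no device-specific information. A later erosion or removal in such a woman cannot be assigned to the index sling rather than the earlier one.
- Section 7 counts a further sling operation as a re-operation outcome. Without the prior-SUI exclusion, the same operation could be both one record's outcome and a new index surgery.

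**Code lists.** Section 4 says the study spans the ICD-9 and ICD-10 eras. The appendix row for urethral fistula pairs ICD-9 599.1 with ICD-10 N36.0. The Section 5 exclusion cites 599.1, 599.2 and 619.0 and no ICD-10 code, so as written it names nothing to search for in the ICD-10 years.

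**Look-back, conditional on pre-start records being unavailable.** A surgery at the start of 2010 would have 0 months of observed history and one at the end of 2010 nearly 12; at Yale the same holds for 2013. The prior-surgery rules have no time limit, so for them look-back keeps growing. A January 2011 surgery has 2011 − 2010 = 1 year and a January 2018 surgery has 2018 − 2010 = 8 years (2018 − 2013 = 5 at Yale).

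**The case against.** The best reply is that each version is workable alone, that reporting is descriptive with no direct mesh versus non-mesh comparison, and that under the synopsis the sensitivity analysis already removes women with prior surgery. This is fair. The cohort is not undefined; it is defined twice. But descriptive rates still need one denominator, and the reply assumes that the synopsis governs, which the protocol does not say.

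A reader might infer more than the document supports:

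- *That the five sites will build different cohorts.* Section 6 has the Vanderbilt site write the transformation code for all sites. The likelier risk is one unstated choice applied everywhere.
- *That the sensitivity analysis is the only check on missed outcomes.* Section 6 also plans chart review of 50 to 100 cases per site and comparison with the curated Mayo series. These are not described as capturing care received elsewhere, but they are checks on outcome data.
- *That the two cohorts would be identical under Section 5.* The visit wording differs, so near-identical is as far as the text goes.
- *That all first-year surgeries are misclassified, in a proportion that can be computed from the site volumes.* The 2010-2019 range in Section 5 can be read as the window for index surgeries, and nothing says earlier records cannot be queried, although the synopsis entry on data captured points the other way. Even without earlier records, a late-2010 surgery has nearly a full year. The volumes are raw CPT 57288 counts without year-by-year figures, so a proportion would rest on assumed even volumes.

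**Conclusion.** The contradiction stands. Both texts are current, they cannot both describe the main cohort, and the protocol gives no rule of precedence. The consequence is either a nearly redundant sensitivity analysis or main results that include women with an earlier sling.

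Its size cannot be stated. The protocol does not give the share of women without a prior-year visit or with prior prolapse or SUI surgery, and the preliminary volumes come before any exclusion. Nor does the document show that Section 5 is the right main cohort; that is for the study team to decide.

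The ICD-9-only exclusion is a separate and smaller defect that stands on the text as written. The look-back problem is conditional: it arises only where records before a site's data start cannot be used.

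**What to change.** Before extraction:

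1. Name one main cohort and make the other version the sensitivity cohort, so that the two differ. Section 5 as main with the unrestricted cohort as sensitivity would serve, and so would the reverse.
2. Use one visit definition, with the same specialties and the same anchor date, wherever the rule appears.
3. Align the synopsis with Sections 4, 5 and 9, and say whether the fistula/diverticulum exclusion applies to both cohorts.
4. Add ICD-10 equivalents to that exclusion, starting from the pair already in the appendix.
5. State for each site whether records before its data start (2010; 2013 at Yale) can be queried. If not, flag first-year surgeries as having incomplete look-back and repeat the results without them. This secures at least 12 months for the visit rule. It does not equalise look-back for prior surgery, and the text should say so.

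The cost is wording, a revised code list, a flag in the shared code and one extra run. Leaving out first-year surgeries removes the women with the longest potential follow-up and part of the overlap with the curated 2010-2012 Mayo data, which is a reason to do it as a check rather than in the main analysis.

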- Chronic clinical conditions will be aggregated using the Healthcare Cost and Utilization Project's Clinical Classification Software, which reduces all ICD-9/10 codes to 285 clinically meaningful groups⁴². The CCS has been updated to include ICD-10, which is important, as this project will span ICD-9 and 10 eras.
- Medication exposures will be aggregated using the PCORNet⁴³ instantiation of the RxNorm controlled vocabulary⁴⁴ and leveraging this vocabulary to the Anatomical Therapeutic Chemical (ATC) Level 4 groupings, which are clinically relevant drug classes.

Some co-variates may not be ascertainable in some participating sites' PCORNet CDM instances, and this will be explored and reported. Each of the outcomes, exposures, and covariates will be analyzed for counts in each site and a summarization and report will be provided to characterize the data at each site. Stratified reporting of those receiving surgery for SUI with mesh and those without mesh will be performed.

Next, if the characterization of the data is sufficient for the task, we will pursue a Cox proportional hazards model analysis, with each of the outcomes assessed from the time of the surgery as a time-to-event. We will censor the time-to-event analysis with death or loss to follow-up, defined as a time period

Version 2.0

[15 July 2020]

>2 years from last applicable encounter of primary care, Obstetrics & Gynecology, or Urology. The models will be executed at each institutional separately using LASSO Cox to determine the consistently included covariates in each institution⁴⁵. We will then use the final variable list and utilize the method described by Lu and colleagues that uses a distributed analysis approach to obtain an exact model solution without sharing case level data (only intermediate and aggregate model coefficients and matrices)⁴⁶.

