7. STUDY OUTCOMES

The primary outcomes of interest are:

- Re-operation (revision, incision, excision, removal) or mesh removal
- Chronic pain, defined as pain persisting at least three months after surgery⁴⁹
- Voiding symptoms, defined as recurrence of incontinence or new retention.

All outcomes are determined in the surveillance period after surgery. Re-operation or mesh removal is defined as a surgery for any kind of mid-urethral sling, urethral bulking agent, bladder neck pubovaginal sling (autologous or allograft), or revision for mesh exposure. Resumption of voiding symptoms was defined as subsequent urinary retention, urinary incontinence, and sling revision for urinary retention. Chronic pain is defined as a new post-operative pain score >3 of 10 on vital sign data occurring over at least 3 months or greater of duration, or diagnosis codes related to abdominal and pelvic pain.

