9. STATISTICAL ANALYSIS PLAN (SAP)

9.1 STATISTICAL METHODS

Each of the outcomes, exposures, and covariates will be analyzed for counts at each site and a summarization and report will be provided to characterize the data. Stratified reporting of those receiving surgery for SUI with mesh and those without mesh will be performed. While this will allow for indirect comparison of these sub-populations side by side, no direct statistical comparisons between the groups will be made.

Next, if the characterization of the data is sufficient for the task, we will pursue a Cox proportional hazards model analysis, with each of the outcomes assessed from the time of the surgery as a time-to-event. We will censor the time-to-event analysis with death or loss to follow-up, defined as a time period >2 years from last applicable encounter of primary care, Obstetrics & Gynecology, or Urology. The models will be executed at each institutional separately using LASSO Cox to determine the consistently included covariates in each institution²⁵. We will then use the final variable list and utilize the method described by Lu and colleagues that uses a distributed analysis approach to obtain an exact model solution without sharing case level data (only intermediate and aggregate model coefficients and matrices)⁴⁶.

Because bootstrapping combined with the distributed analysis method would be computationally intensive, we will utilize 10-fold cross validation across all sites for internal validation of the risk model. We will assess overall discrimination using Harrell's concordance statistic (C-statistic)⁴⁷. To provide calibration assessments, we will also evaluate the model at fixed time points of 1 year and 2 year for each outcome using the AUC and the Estimated Calibration Index (ECI)⁴⁸. The ECI looks at the squared difference between the predicted probability and an estimated observed probability, ranging between 0 and 100, with 0 meaning perfect calibration. Additionally, we will graphically analyze calibration by investigating the smoothed observed-to-predicted probability plot⁴⁸.

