13. APPENDICES

Synthetic Mid-Urethral Slings for Stress Urinary Incontinence in Women Appendix: Data Collection

Category	Name	Definition, structured?	CDM?	Notes
Covariate	Age @ Procedure	Age as difference between date of surgery and date of birth	Yes- derived to remove PHI	
Outcome	Date of Death	The date on which the patient died.	Yes	Capture as date/time Lahey Comments: Captured only within institution, working on linkage to the SSI Death Index, otherwise would need chart review. Death status is more easily ascertained but not the death of death.
Inc/Excl Criteria	Surgery Indication (POP vs SUI)	Structured Codes Include Sling CPT: 57288 Include Lap sling CPT: 51992	Yes	CPT: 57288 includes retropubic midurethral slings, transobturator slings, and minislings,

Protocol 1				[15 July 2020]
				single-incision sling, adjustable sling CPT: 51992 includes laparoscopy approach.
Exposure	Mesh Implantation	Yes/No	Yes	Key Exposure
Covariate	Gender	Gender	Yes	
Covariate	Race	White, Black or African American, American Indian or Alaska Native, Asian, Native Hawaiian or Other Pacific Islander	Yes	
Covariate	Ethnicity	Hispanic or Non-Hispanic	Yes	
Covariate	Women's Health History: pregnancies, vaginal deliveries, and menopausal status ⁵²	Look for Gravida/Parity in problem list: ex: G3P3? Possible administrative codes: Grand multipara status only (not pregnant) ICD9/10- V61.5/Z64.1 Grand multiparity SNOMED- 364325004/452221000000100/ 440681000000102 # Parity LOINC- 11977-6 Unspecified menopausal and post-menopausal disorder ICD 9/10 627.9/N95.9 Premature menopause ICD9/10 256.31/E28.31 Post-menopausal bleeding ICD 9/10 627.1/N95.0	Partial, Admin Codes	May miss portion of data if admin codes only

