		 Mesh exposure and erosion (ICD9/10 629.31, 629.32/T83.711, T83.721) Urinary Retention (CPT Code 53500, ICD 9/10 788.20, 788.21/R33.0, R33.8-R33.9) Urgency of urination (ICD9/10 788.63/R39.15) Urge incontinence (ICD9/10 788.31/N39.41) Bowel injury (ICD9/10 569.83/S36) Bladder/urethral injury (ICD9/10 596.6,867.0/S37) Infection (ICD9/10 686.9,998.5,999.3,998.51,998.59/T81) Retropubic hematoma (ICD 9/10 568.81,,568.81,459.0/K66.1) Retopubic hematoma (ICD 9/10 568.81,,568.81,459.0/K66.1) Retopubic hematoma (ICD 9/10 568.81,568.81,459.0/K66.1) Bulking Injection CPT 51715, ICD 9/10 59.72/ PCS 3E0K3GC Laparoscopic Retropubic Urethropexy CPT 51990, 51992, 51999 Abdominal Retropubic Urethropexy CPT 51840,51841 Needle Bladder Neck Suspension CPT 51845 Kelly plication CPT 57220 Cystourethroplasty CPT 51800 Subtypes: Stress incontinence, female/mixed incontinence (ICD9/10 625.6,788.33/N39.46) Stress incontinence (female) (male)(ICD10 CM N39.3) 		
Outcome	Mesh Removal	 General, CPT 57287-Removal or revision of sling for stress incontinence (fascia or synthetic) ***some erosions managed surgically may have been coded by a different CPT (i.e. 57295 revise vaginal graft via vaginal approach) and not CPT 57287, which indicates a sling revision/removal. 	Yes	Possible Options: (a surgery for any kind of mid-urethral sling, urethral bulking agent, black neck pubovaginal sling (autologous or allograft), or revision for mesh exposure). Represented as a Date, allows time-to-event analysis.
Outcome	Post-Procedural Pain	?, mix of vital sign (pain score >3 of 10 on vital sign data) and likely free text. Also, diagnosis codes related to abd/pelvic pain (if prior pain free).	Some portion	Would have to exclude prior chronic pain or detect specific mention of new pain (free text). Could analyze group with no pre-surgical pain,

Protocol 1				[15 July 2020]
				otherwise probably beyond scope. Date/Time of first post- op occurrence.

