Outcome	Mesh Erosion	Admin Codes: ICD-9-CM codes for mesh erosion: 996.30, 996.39, 996.59, 996.60, 996.65, 996.69, 996.70, 996.76, 996.79, 939.0, 939.2, and 939.9 ICD 10 CM: T83.498A, T85.698A, T85.79XA, T83.598A, T85.79XA, T85.9XXA, T83.89XA, T85.898A, T19.0XXA, T19.2XXA, T19.9XXA Surgical Complications: ICD 9/10 629.31/T83.711 Erosion of implanted vaginal mesh ICD 9/10 629.32/T83.721S Exposure of implanted vaginal mesh ICD 9/10 996.76/T83.9 Complication of genitourinary device, implant or graft ICD9/10-PCS V58.2/30233N1, 30233P1, 30233H1 Blood transfusion ICD9/10 998.5/ T81.49XA, T81.40XS, T81.41, T81.43, T83.5, T83.6 Postoperative infection ICD 9/10 778.2/R33.9 Urinary retention		Capture as date/time Exclude 629.3- complication of implanted vaginal mesh and other prosthetic materials, 629.31- erosion of implanted vaginal mesh, or 629.32-exposure of implanted vaginal mesh because these ICD-9 were not released until 2011? ²⁸ SME determined that topical estrogen could be prescribed for other reasons
Outcome	Urethral fistula	Admin Codes ICD 9- 599.1 ICD 10-N36.0	Yes	Capture as date/time
Covariate	Prior Abdominal Surgery Or Pelvic Radiation	Admin Codes: Personal history of irradiation-V15.3/Z92.3, Irradiation cystitis- N30.4	Yes	Yes/No
	Therapy	CPT/ICD 9/ICD 10 for prior abdominal surgery:		

Protocol 1		[15 July 2020]
	Hysterectomy: 00846, 00855, 00944, 01962,	
	01963, 01969,45126, 51597, 51925, 56308,	
	58150, 58152, 58180, 58200, 58205, 58210,	
	58240, 58260, 58262, 58263, 58265, 58267,	
	58270, 58275, 58280,	
	58285, 58290, 58291, 58292, 58293,	
	58294, 58541, 58542, 58543, 58544,	
	58548, 58550, 58552, 58553, 58554,	
	58570, 58571, 58572, 58573, 58575,	
	58951, 58953, 58954, 59135,	
	59525, 59560, 59561, 59580, 59581	
	/68.9/290.711	
	Cesarean section: 00850, 59500, 59501,	
	59520, 59521, 59540, 59541/649.81/075.82	
	Appendectomy: 44950, 44955, 44960,	
	44970, 49315, 56315/V45.79/Z90.89	
	Hernia repair: 49505, 49507, 49520,	
	49521, 49525, 49550, 49553, 49555,	
	49557, 49560, 49561, 49565, 49566,	
	49570, 49572, 49585, 49587, 49590,	
	49650, 49651, 49652, 49653, 49654,	
	49655, 49656, 49657, 49659/53.5/0WQF0ZZ,	
	0WQF3ZZ, 0WQF4ZZ	
	Cholecystectomy: 47562, 47563, 47564, 47600,	
	47605, 47610, 47612, 47620/51.0-	
	51.04/0FT40ZZ	
	51.04/01 14022	
	Colectomy: 44139, 44140, 44204, 44205, 44206,	
	44141, 44143, 44144, 44145, 44146, 44147,	
	44150, 44151, 44157, 44158, 44160,44320,	
	44322, 44799, 45110, 45111, 45112, 45113,	

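### The Section 5 exclusion for urethral diverticulum or urinary-genital fistula lists only ICD-9 codes, so in a 2010-2019 cohort eligibility depends on the coding era

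*Protocol*

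**What the plan says.** The exclusion criteria in Section 5 remove women who, in the 90 days before the index operation, had a diagnosis of "urethral diverticulum ICD-9-CM code 619.0 or any urinary-genital tract fistula (codes 599.1 and 599.2". The inclusion criteria in the same section set the period: "EHR-Based study date range 2010-2019". Section 4, explaining why its grouping of chronic conditions must handle both code systems, adds "as this project will span ICD-9 and 10 eras".

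Two rows of the data collection appendix (Section 13) bear on this:

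- The row tagged as an inclusion/exclusion criterion concerns the surgical indication and holds procedure codes only: "Structured Codes Include Sling CPT: 57288 Include Lap sling CPT: 51992".
- Urethral fistula has a row of its own, tagged as an outcome to be captured as a date and time, with the codes "ICD 9- 599.1 ICD 10-N36.0".

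**The concern.** An exclusion defined by codes works only for the code systems it lists. This one lists a single system, while the cohort uses two. A woman whose fistula was coded 599.1 a month before surgery is excluded. A woman with the same condition coded N36.0 is kept. Eligibility then changes with calendar time for a reason unrelated to the patient. The change reaches every outcome, because it alters who is in the cohort.

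Section 6 has one site write the transformation code for all sites, so a literal reading of the list would be repeated at all five.

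**Working it through.** **Step 1: compare the code lists.**

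| Place in protocol | ICD-9 | ICD-10 | Purpose |
|---|---|---|---|
| Section 5, exclusion | 619.0, 599.1, 599.2 | none | eligibility, 90-day look-back |
| Section 13, inclusion/exclusion row | none | none (CPT 57288, 51992 only) | identifying the operation |
| Section 13, urethral fistula row | 599.1 | N36.0 | outcome |

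The exclusion has three ICD-9 codes and no ICD-10 code. Codes 619.0 and 599.2, and the term diverticulum, occur nowhere else in the protocol. N36.0 occurs only as an outcome code. The grouping software that Sections 4 and 6 say covers ICD-10 serves the chronic-condition covariates, not eligibility. Nothing elsewhere fills the gap.

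**Step 2: how much of the caseload is exposed.** The protocol states no figure to reproduce and no changeover date. I assume late 2015 (2015.75) and vary it by one year each way. Inputs from the Synopsis, Description of Sites/Facilities:

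- Vanderbilt: 6,106 slings in 2010-2018, about 500 a year recently.
- Mayo: 5,413 in 2010-2018, about 500 a year recently.
- Weill-Cornell: 887 in 2010-2019, 150 a year recently.
- Total: 6,106 + 5,413 + 887 = 12,406.

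The other two sites give no totals and are left out. Exposed operations = recent yearly volume × years from the assumed changeover to the end of that site's count.

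- 2015.75: 500 × 3.25 + 500 × 3.25 + 150 × 4.25 = 1,625 + 1,625 + 637.5 = 3,887.5; 3,887.5 / 12,406 = 31.3%.
- 2014.75: 2,125 + 2,125 + 787.5 = 5,037.5; 5,037.5 / 12,406 = 40.6%.
- 2016.75: 1,125 + 1,125 + 487.5 = 2,737.5; 2,737.5 / 12,406 = 22.1%.

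The yearly volumes are averages over the last four years, so the earlier dates stretch them slightly. The totals come from a raw query on one procedure code before any exclusion, and their windows differ by site. The percentages show how much of the caseload the list may not cover, not how many women are misclassified. The protocol gives no prevalence of diverticulum or fistula, so that number cannot be computed.

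**Step 3: the fistula outcome, taken separately.** A woman with a fistula before surgery can stay in the cohort by two routes:

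- Her diagnosis is coded N36.0 within the 90 days and matches nothing on the list.
- Her diagnosis, in either system, was last coded more than 90 days before surgery, for example 599.1 at day -100.

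Adding ICD-10 codes closes the first route and leaves the second open. The fistula row states no condition about fistula before surgery, so a repeat code afterwards could be counted as a new event.

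**The case against.** **The criterion also names the conditions in words.** A programmer could reasonably add the ICD-10 codes, and final code sets are often settled in a later specification. This stands in part. It is why one should not infer that the exclusion removes no one in the ICD-10 era. Even run literally, an operation within 90 days after the changeover can still have an ICD-9 code in its look-back. But the protocol does more than leave detail for later: it fixes a list, and the list is incomplete for the period it governs.

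**Fistula is a marginal outcome.** It is absent from the aims in Section 3 and from the primary outcomes in Section 7. The Section 7 sentence "All outcomes are determined in the surveillance period after surgery" directly follows those primary outcomes. Section 9.1 says "Each of the outcomes, exposures, and covariates will be analyzed for counts at each site" without saying whether every appendix row is meant. This stands, so the remark on the fistula outcome is conditional on its being reported.

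**Tempting further readings.**

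- A reader might infer that the ICD-10 gap is what lets old fistulas be counted as new. It is one route only; the 90-day window leaves the other open with complete codes.
- A reader might contrast the appendix's pain row, which has "diagnosis codes related to abd/pelvic pain (if prior pain free". That row is openly tentative: its definition opens with a question mark and its notes doubt the scope. It sets no settled standard.
- A reader might conclude that the fistula outcome list should be widened. The documents do not show that 599.1 and N36.0 miss anything.

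**Conclusion.** The point holds as a minor defect in an eligibility rule. Section 5 lists three ICD-9 codes and no ICD-10 code for a cohort that the protocol itself says spans both systems. Applied as coded, eligibility differs by coding era. That part rests on the text alone.

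The size is uncertain. About 31% of operations at three sites are exposed (22% to 41%), on an assumed changeover date and approximate yearly volumes. It would be wrong to read this as a share of the cohort wrongly included. The number of women with such a diagnosis in the look-back is unknown and, in my judgement, probably small. No bias in any outcome rate has been shown.

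**What to change.** Add N36.0 and the ICD-10 counterparts of 619.0 and 599.2 to the Section 5 exclusion, after checking them against the code book. State that the criterion applies in both code systems.

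Separately, if urethral fistula is reported as an outcome, count it only in women with no fistula code in either system at any time before surgery in the available record. A 90-day look-back does not do this.

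The cost is one edit to a code list and one added condition on an appendix row. Section 8.1 says that ICD-9 and ICD-10 condition codes are available at all sites, so no new data are needed.
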